Phase I, Clinical Analog Trial with A-B-A phase design.

**Description of
Sites/Facilities Enrolling
Participants:**

This study will take place in Greater Inland Northwest area in cooperation with the Community Health Association of Spokane (CHAS) and other clinical referral entities throughout the Spokane region, including MultiCare Health System (MHS) and others.

Description of Study

Intervention/Experimental Manipulation: We will utilize an A-B-A, completely within-subject design with the intent of recruiting twenty (n=20) total participants.

During the first A phase, participants will receive reinforcement for simply submitting breath samples three times per day between 4 and 6 hours apart. In this application, we will use a Bluetooth enabled breathalyzer developed by BACtrack, however our smartphone-based technological solution will interact with any alcohol monitoring device, such as BACtrack Skyn.

During the B phase, the delivery of reinforcers will be contingent upon the submission of an alcohol negative breath sample on an escalating schedule.

The A phase or return to the baseline phase will involve the delivery of reinforcers for simply submitting a breath sample during the designated windows of time. We will also collect EMA data on stress, anxiety, depression, and other brief measures daily through their smartphone.

Each phase will last a total of four weeks (i.e., two weeks of the first A phase, four weeks of the B phase, and then two more weeks of the A-phase) each for a total of 8 weeks of participation. To the extent possible, we will use existing protocols, procedures, and equipment that we have used in previous A-B-A studies.

Study Duration*: Eight to twelve months.

Participant Duration: Two months for each participant to complete all study-related tasks.

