3 OBJECTIVES AND ENDPOINTS

Primary Objective:

To develop and combine mobile technology, geospatial mapping, and biomarker measurement, with individual goal setting and EMA feedback to launch behavioral modification strategies and progress monitoring.

Secondary Objectives:

To develop and consumer-test the mobile application component to help the patient alcohol-related treatment goals at home.

Primary Endpoint:

Biochemically confirmed alcohol abstinence measured thrice daily throughout the 8-week study.

Secondary Endpoints:

The secondary endpoint will include self-reported alcohol use measured by the Timeline Follow Back to assess the frequency and amount of daily drinking via multi-modal EMA data collection.

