5 STUDY POPULATION

5.1 INCLUSION CRITERIA

To be eligible to participate in this study, an individual must meet all the following criteria:

- 1) Age 18-65 years.
- 2) An Alcohol Use Disorders Identification Test (AUDIT) score of 8 or higher.
- 3) Ability to read and speak English.
- 4) Ability to provide written informed consent.
- 5) Breath alcohol of 0.00 during informed consent.
- 6) Operate a smartphone with an active service provider.

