5.5 STRATEGIES FOR RECRUITMENT AND RETENTION

We anticipate a 5-month recruitment period, necessitating n=4 recruited per month which is far below our normal recruitment rates. Flyers will advertise the study, and staff and providers will be aware of the study and will be asked to refer potentially interested participants to our investigation. As noted elsewhere, while

we will partner with clinics we will also recruit from the community. After an initial phone screening, those deemed eligible will be scheduled for an in-person study interview, during which they will provide informed consent and complete baseline data collection. During this time, participants will also receive a brief tutorial on how to use the BACtrack breathalyzer and how it integrates with the application on their smartphone. Participants who do not have a compatible iPhone Operating System (iOS) smartphone will be provided one for this study. The phones will be supplied from a testing inventory maintained by Managed Health Connections.

Participant set-up instructions will also describe the time window for reporting the definition of zones of use and will be provided contact information for technical support to be used during the study. During the baseline visit participants will receive a \$30 gift cards for their time.

During the first A phase, participants will receive \$2 per sample (regardless of being positive or negative for breath alcohol) submitted instantly, for a maximum payout of \$6 per day.

During the B phase, participants will begin by receiving \$2 per alcohol negative breath sample submitted, escalating by \$0.25 per alcohol negative breath sample submission until a maximum value of \$3.50 per sample is reached. Once this value is reached based on negative breath sample submissions, participants will continue to receive \$3.50 per alcohol-negative breath sample submission. If a participant submits an alcohol positive breath sample, they will be reset to \$2.00 per sample and will need to work up to receive \$3.50 per sample again. Final onetime payment of \$50 will be provided to participants upon return of study devices. Participants will receive electronic payment through a gift card. Payments will be loaded onto the card weekly.

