10.1.1.2 CONSENT PROCEDURES AND DOCUMENTATION

The consenting process will be conducted consistently for every participant.

If a participant is eligible, the iPad that was used for screening will display the consent form. The research assistant (RA) or research coordinator (RC) will explain that this document will explain the details of the study they are being asked to take part in. Allow the participant plenty of time to read.

When the participant is done reading the consent, they will be asked if they have any questions about the study. If the answer to a question is not immediately obvious, the research coordinator or an investigator will be asked for their opinion, which must also be documented. The consent form will then be thoroughly reviewed to ensure that the participant understands what they are agreeing to.

Eligibility for the study is determined by study procedures. Signing the consent does not ensure eligibility to participate. That said, it will be made clear to the prospective participant that participation will not impact their care.

The key point to stress in the consenting process is that **PARTICIPATION IS VOLUNTARY**. Participants can choose not to consent to the study or discontinue at any time for any reason. They can choose not to answer any questions that make them feel uncomfortable.

The RA/RC will show the participant where to type their name and date the consent form. The participant must date and place their signature or initials on consent. The RA/RC will give a paper copy of the consent to the participant for their records.

Remember that consenting is an ongoing process.

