| 17 | I have the resources necessary to use the system. | | | | | | | |
| 18 | The system is not compatible with other systems I use. | | | | | | | |
| 19 | I have the knowledge necessary to use the system. | | | | | | | |
| 20 | A specific person (or group) is available for assistance with system difficulties. | | | | | | | |
| 21 | I could complete a job or task using the system... | | | | | | | |

| | | | | | | |
|------|---------------------------------------------------------------------------------------------------------|--|--|--|--|--|
| 21.a | If there was no one around to tell me what to do as I go. | | | | | |
| 21.b | If I could call someone for help if I got stuck. | | | | | |
| 21.c | If I had a lot of time to complete the job for which the software was provided. | | | | | |
| 21.d | If I had just the built-in help facility or assistance. | | | | | |
| 22 | I hesitate to use the system for fear of making mistakes I cannot correct. | | | | | |
| 23 | It scares me to think that I could lose a lot of information using the system by hitting the wrong key. | | | | | |
| 24 | I feel apprehensive (anxious) about using the system. | | | | | |
| 25 | The system is somewhat intimidating to me. | | | | | |
| 26 | I plan to use the system in the next <n> months. | | | | | |
| 27 | I predict I would use the system in the next <n> months. | | | | | |
| 28 | I have used the system a lot in the past 4 weeks. | | | | | |
| 29 | I have been using the system regularly in the past 4 weeks. | | | | | |

Phone Screening Script:

Research staff will call potential participants and will greet and present themselves to participants. When appropriate in the conversation, they will use the following script:

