"We have a research Study that is testing the usefulness of an application based psychosocial treatment called Contingency Management that uses a mobile application to see if it can improve alcohol secession treatment response by reducing the days of heavy alcohol use. This intervention involves sending remote alcohol breathalyzers samples (via mobile phone) and getting paid if samples have alcohol levels below (Blood Alcohol Concentration "BAC") 0.08. The study is titled: **"Automated Contingency Management System for Reduction of Alcohol Use. The National Institute on Alcohol Abuse and Alcoholism funded this study, and the Washington State University Institutional Review Board has approved it. The study looks at the ability of this technology to help individuals to reduce the number of days of heavy alcohol use for eight weeks. If you are interested and qualify, we will set a 2 hours in-person interview in a date and time that is convenient for you. People who take part will receive up to \$536.75 for 8 weeks of participation to compensate for their time.**

Would you be interested in answering a few questions to see if you qualify for the study?

→ **If no** "Thank you so much for your time, have a wonderful day"

→ **If yes** “Great! Do you have time now to go over the screening questions”?

→ **If no** “Can I call you another time?”

Write the number here: _____

→ **If yes (Handoff to the research recruiting team)**

Great! Now I am going to ask you the screening questions. Some of the questions might be sensitive in nature because they are about your current alcohol use behavior. We ask that you be as honest and accurate as possible. You do not have to answer any question that you do not wish to answer. However, if you choose not to answer some questions, you may not be eligible to take part in the study, because your answers are needed to determine if you are a match.

SD1. How old are you? _____ years

If under 18 or older than 65 years → ineligible, stop screening

SD2. Do you know how to use a smartphone ?

If no→ ineligible, stop screening

If yes→ Do have an iPhone?

If yes→ Is your iPhone an iPhone 7 or newer version with an iOS 13.5?

If no→ If you do not have an iPhone 7 or newer, we can loan you one if you know how to use it, but it must be returned at the end of the study. Upon completion of or withdrawal from the study AND return of the phone you will receive a \$50 Amazon gift card.

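### The phone script says samples are paid when BAC is below 0.08, but the protocol body pays B-phase samples only if alcohol negative and puts no number on negative

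*Protocol*

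**What the plan says.** Section 12 introduces the Phone Screening Script by saying that, when calling potential participants, staff reach a point where "they will use the following script". The script describes the intervention as sending breathalyzer samples remotely and "getting paid if samples have alcohol levels below (Blood Alcohol Concentration 'BAC') 0.08". It draws no distinction between phases, and it gives a maximum payment of $536.75.

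The body states a different rule. Section 1.1 says that in the B phase "the delivery of reinforcers will be contingent upon the submission of an alcohol negative breath sample on an escalating schedule", and Section 4.1 repeats this. Section 5.5 sets the B-phase schedule: $2.00 for the first negative sample, rising by $0.25 per negative sample to $3.50. It adds: "If a participant submits an alcohol positive breath sample, they will be reset to" $2.00. First A-phase samples earn $2 each, "regardless of being positive or negative for breath alcohol". Section 4.1 makes second A-phase reinforcement depend on submission alone.

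The primary endpoint in Section 3 is "Biochemically confirmed alcohol abstinence measured thrice daily throughout the 8-week study". The only other breath-alcohol number in the protocol is in Section 5.1: "Breath alcohol of 0.00 during informed consent". That is an eligibility condition at one visit and does not define a negative study sample.

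**The concern.** In contingency management the payment rule is the intervention. Here the first description a candidate hears is of a scheme that pays for drinking as long as the reading stays under 0.08, while the design sections describe a scheme that pays for no alcohol. The script also presents the study's aim as fewer days of heavy drinking, so 0.08 could sound deliberate to staff and candidates alike.

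The body does not settle the matter with a number. Anyone who configures the app, or answers a participant who asks what counts as negative, finds exactly one numeric payment threshold in the protocol, and it is the one that conflicts with abstinence. If 0.08 were used, paid samples would no longer be evidence of abstinence. If a stricter cut-off is used, participants recruited on the script would lose money, and be reset, for samples they were told would be paid.

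**Working it through.** **1. Rules side by side, for a reading of 0.05**

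| Phase | Body (Sections 1.1, 4.1, 5.5) | Phone script |
|---|---|---|
| First A | paid, whatever the result | paid because below 0.08 |
| B | on the ordinary meaning of negative: unpaid, and reset to $2.00 | paid |
| Second A | paid for submission | paid because below 0.08 |

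For a reading of 0.10, the script implies no payment in any phase, while the body pays it in both A phases. So the script's rule matches the body's in no phase.

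**2. Is it the same payment scheme?** The inputs are the 2-4-2 week phases and three samples a day (Section 4.1), and the $30 baseline payment, $2 A-phase rate, B-phase schedule and $50 device-return payment (Section 5.5). Section 5.5 states the $2 rate only for the first A phase. Carrying it to the second A phase is an inference, supported by the match below.

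- Each A phase: 14 × 3 × $2 = $84.
- B phase: 28 × 3 = 84 samples. The first six earn 2.00 + 2.25 + 2.50 + 2.75 + 3.00 + 3.25 = $15.75. The other 78 earn 78 × 3.50 = $273.00. The total is $288.75.
- Overall: 30 + 84 + 288.75 + 84 + 50 = **$536.75**, the script's figure exactly.

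The script therefore quotes the maximum of the Section 5.5 schedule beside a different qualifying rule. The maximum assumes that every B-phase sample is paid, so it is the same under any cut-off and cannot show which one applies.

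**3. What the difference is worth to a participant.** Assumptions: any reading above 0 is positive (not stated in the protocol), and all 84 B-phase samples are submitted.

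*One sample between 0 and 0.08.* At the plateau, with at least six negatives after it, the loss is the sample itself plus the shortfall while the value climbs back: 3.50 + (1.50 + 1.25 + 1.00 + 0.75 + 0.50 + 0.25) = 3.50 + 5.25 = $8.75. This applies at samples 7 to 78, which is 72 of the 84 positions. At samples 1 to 6 the loss is $3.50, $5.00, $6.25, $7.25, $8.00 and $8.50. At samples 79 to 84 the same values run in reverse. Under the script the loss is $0.

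*Repeated patterns.* The last sample of the day falls in the band and all others are negative. Each week then starts again at $2.00, so the weeks are identical.

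| Days affected | B-phase earnings under Section 5.5 | Loss against $288.75 |
|---|---|---|
| Day 7 each week | 4 × (15.75 + 14 × 3.50) = 4 × 64.75 = $259.00 | $29.75 (10.3%) |
| Days 6 and 7 each week | 4 × (15.75 + 11 × 3.50 + 2.00 + 2.25) = 4 × 58.50 = $234.00 | $54.75 (19.0%) |
| Every day | 28 × (2.00 + 2.25) = $119.00 | $169.75 (58.8%) |

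Under the script every row earns $288.75.

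**4. Range over the unstated cut-off.** If the cut-off lies below the sample's reading, the losses above apply. If it is 0.08, payment does not differ at all. For 20 participants the rule governs up to 20 × 84 = 1,680 B-phase payment decisions. The protocol gives no distribution of readings, so the share falling between 0 and 0.08, and any effect on the endpoint, cannot be calculated.

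**The case against.** The best counter-argument is that this is one stray sentence. Three body sections agree on alcohol negative, and nearby appendix pages carry a Version 0.1 header although the protocol is Version 1.1, which is compatible with leftover text. Candidates later attend in person, receive a tutorial on the breathalyzer and app, and go through consent: "The consent form will then be thoroughly reviewed to ensure that the participant understands what they are agreeing to". The app dashboard in Section 8.2 then shows progress toward rewards. These steps limit the harm of a wrong statement at first contact, and the consent form, which is not shown, may state the rule correctly. This stands as a limit on the consequences. It does not remove the sentence from the current protocol, where it is the text to be read out.

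A second objection is logical: if negative is undefined, 0.08 cannot be proved wrong, and if negative plainly means no alcohol, the body already resolves the conflict. Either way the text needs correcting. On the plain reading, the script misstates B-phase payment. On the other reading, the contingency pays for something other than the abstinence that the primary endpoint is meant to confirm. The script is wrong about the A phases on both readings.

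Third, the cut-off for scoring the binary endpoint may properly sit in an SAP. That is accepted, and its absence here is not part of the complaint. An SAP would not set what candidates are told or which samples are paid and reset.

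Finally, the dollar losses rest on assumed drinking patterns and an assumed zero cut-off. They illustrate the difference and are not forecasts.

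**Conclusion.** The point holds. The script gives candidates a payment threshold that does not fit the B-phase contingency in Sections 1.1, 4.1 and 5.5, or payment for submission in the A phases. The body supplies no number to override it. What is established is a misstatement to candidates and an unresolved conflict over which samples earn payment. A misdelivered intervention is not established, because nothing shows how the app is set.

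The size depends on the unstated cut-off. It is zero if the cut-off is 0.08. If any reading above 0 is positive and submission is complete, it is $8.75 for an isolated sample at 72 of 84 positions, and up to $169.75 of $288.75 for the daily pattern. No effect on the endpoint is claimed. This should be fixed before enrolment, because the threshold in question decides delivery of the intervention itself.

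**What to change.** Replace the 0.08 sentence in the script with wording that says B-phase samples are paid only if alcohol negative and A-phase samples are paid whatever the result. In Section 5.5, state one numeric cut-off for a negative sample (0.00, as at consent, is the obvious candidate) and apply it to both B-phase payment and the reset. Carry the same number into the abstinence score, wherever that is defined, so that a paid sample and an abstinent sample mean the same thing. Confirm the app's setting against that number, and check that the consent form agrees.

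The cost is a wording amendment with IRB approval and a configuration check before enrolment. No extra data, visits or participants are needed, since breath alcohol is already scheduled three times a day (Section 8.1, Table 2), and the $536.75 maximum does not change.

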
[Complete the participant's weekly follow-up questionnaire with them. After filling out the questionnaire, ask,]

Do you have any concerns about your study participation?

[If Yes, note concerns and contact study PI as necessary]

Thank you for taking the time to talk with me today. If you have any additional questions or concerns, please feel free to contact me. My name is and I can be reached at phone number..... and/or [email address.....].
